6. DOSAGE AND ADMINISTRATION

6.1. Study Treatment Administration

For the purposes of this study, ‘study drug’ or ‘study therapy’ refers to both ibrutinib and/or nivolumab. All dosing information must be recorded in the Dosage Administration page of the eCRF. A treatment and study design scheme is provided in [Figure 1](#).

The duration of each treatment cycle is 14 days. Day 1 or start day of a new cycle is triggered by the infusion of nivolumab. The cycle duration may be changed based on decision by the SET (Section 3.3). Study drugs will be administered until disease progression or unacceptable toxicity,

whichever occurs first. On days when both drugs will be administered, the sequence of administration will be nivolumab IV followed by oral ibrutinib.

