6.1.2. Dosing Schedule

Study drugs will be administered as described below in Table 5.

Table 5: Ibrutinib and Nivolumab Dosing Schedule

| | Ibrutinib Run-in, Day -7 to Day 1 | Cycle 1 Day 1 | Cycle 2 Day 1 | Day 1 of every cycle, Cycle 3 and all subsequent cycles |
|---------------------------------|--------------------------------------|---------------------------------|---------------|--|
| | | DLT Determinative Period | | |
| Part A, Cohort A1 and A2 | | | | |
| Ibrutinib | | <-----continuous dosing-----> | | |
| Nivolumab ^a | | 3 mg/kg | 3 mg/kg | 3 mg/kg |
| Part B, Cohort B1 and B2 | | | | |
| Ibrutinib | | <-----continuous dosing-----> | | |
| Nivolumab ^a | | 3 mg/kg | 3 mg/kg | 3 mg/kg |
| Part B, Cohort B3 and B4 | | | | |
| Ibrutinib | | <-----continuous dosing-----> | | |
| Nivolumab ^a | | 3 mg/kg | 3 mg/kg | 3 mg/kg |

^a Nivolumab administered first followed by ibrutinib.

Ibrutinib Run-in Period: In Cohort B1 and B2, to assess pharmacokinetic and pharmacodynamic characteristics of ibrutinib monotherapy, ibrutinib will be given at the recommended Phase 2 dose over an initial period of seven days prior to the first dose of nivolumab (Day -7 to -1).

Nivolumab will be administered on Day 1 of each 14-day treatment cycle.

DLT Period: DLT will be documented over the first 2 cycles beginning with the first concomitant administration of ibrutinib and nivolumab on Day 1 of Cycle 1.

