6.3. Nivolumab Administration

Eligible subjects will receive treatment with nivolumab at a dose of 3 mg/kg given as a 60-minute IV infusion on Day 1 of every 14-day cycle. If the subject's weight on the day of dosing differs by > 10% from the weight used to calculate the dose, the dose must be recalculated. All doses should be rounded to the nearest milligram.

There are no premedications recommended for nivolumab on the first cycle. If an acute infusion reaction is noted, subjects should be managed according to guidelines provided in Section 8.11.

Subjects may receive nivolumab infusions with no less than 12 days between doses and no more than 3 days after the scheduled dosing date. A dose given after the 3-day window is considered a dose delay. A maximum delay of 42 days between doses is allowed.

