1.2. Trial Design

This is an open-label Phase 1/2a study, which consists of Part A (Dose Optimization Cohorts A1 and A2) and Part B (Expansion Cohorts B1, B2, B3 and B4). In the context of this study, a treatment 'cycle' is defined as a course of treatment of 14 days starting with the intravenous administration of nivolumab on Day 1 of each cycle along with once daily oral intake of ibrutinib on all days.

It is anticipated that approximately 158 subjects for both Parts A and B would be enrolled.

Part B (Dose Expansion Cohorts) will be open for enrollment after the RP2D is determined in Part A. In Part B, further assessment of the RP2D will be explored in 4 subject populations to further evaluate the safety and clinical activity of ibrutinib in combination with nivolumab. During the expansion period, subjects with CLL/SLL with del 17p or 11q (Cohort B1), FL (Cohort B2), DLBCL including FL transformed into DLBCL (transformed DLBCL) (Cohort B3), and Richter syndrome (Cohort B4) will be enrolled. Approximately 35 subjects will be

enrolled in each of the expansion cohorts. The subjects will be treated at the RP2D level selected to further assess the safety, pharmacokinetics, pharmacodynamics, pharmacogenomics, and activity of the combination.

The median duration of study therapy is expected to be approximately from 2 (DLBCL) to 15 (CLL) months.

The End-of-Treatment Visit will occur within 30 days after the last dose of ibrutinib or nivolumab, whichever treatment occurred last.

During the Follow-up Period, long-term safety, survival status, disease progression, subsequent anticancer therapy, and occurrence of other primary malignancy data will be collected. During the Follow-up Period, subjects should be followed for safety up to 30 days after the last dose of ibrutinib or 100 days after the last nivolumab infusion, whichever is later. The safety includes adverse event reporting and laboratory assessments (at the first follow up). Thereafter Follow-up visits will be completed approximately every 3 months until death or the end of study. Subjects who have developed treatment-related Grade 3 or higher toxicity at the end of treatment will be assessed until recovery to Grade ≤ 1 or baseline, deemed irreversible, or until end of study. Adverse events leading to discontinuation will be followed up until resolution or return to baseline, or end of study, whichever occur first.

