2.2. Visit Windows

Visit window will be based on phases and cycles:

(For the purposes of this study, ‘study drug’ or ‘study therapy’ or “study treatment” refers to both ibrutinib and/or nivolumab).

Screening: Up to 28 days before the start of any study treatment.

Treatment: Between the date of first administration of study therapy and the date of the last dose of study drug. The treatment stage will be subdivided by cycles. Each cycle is 14 days, starting from the first dose of study drug. The end date of the last cycle is the date of the last dose of study drug received during the study.

End of treatment: within 30 days after the last dose of ibrutinib or 100 days after the last nivolumab. The assessments performed during the ‘End of treatment visit’ will be included in this End of treatment phase.

Follow-up: After the end of treatment till the last assessment for the last subject in the study (e.g. the last follow-up visit or death).

Baseline assessment is defined as the last non-missing results on or before the first dose of study therapy.

1. Cycle-based analysis may be performed for safety parameters during the treatment up to date of last dose of ibrutinib + 30 days, and last dose of nivolumab +100 days. For the analysis of laboratory measurement by cycle, the mean values within each cycle will be used. For the analysis of laboratory grade by cycle, the worst grade within each cycle will be used.

Assessments will be presented chronologically by cycle day or study day, which are defined as the follows:

Day 1 = date of first dose of study drug / Cycle 1 day -7 (subjects with run-in)

Study Day (if on or after date of first dose) = assessment date – date of first dose +1

Study Day (if before date of first dose) = assessment date – date of first dose

Cycle Day = assessment date – date of first dose for the cycle +1

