3.4. Extent of Exposure

Extent of exposure for ibrutinib will be summarized for the safety population by disease type and study cohorts. Descriptive statistics (n, mean, standard deviation, median, and range) will be provided for total number of cycles, treatment duration (the interval between date of first dose and date of last dose), and ibrutinib dosing information including total dose received (the sum of administered doses), dose intensity (the ratio of total dose and treatment duration).

Dose reduction for ibrutinib is defined as administered planned lower dose level. There is a one applicable dose level reduction for CLL/SLL cohort: 280 mg/day (level 1 reduction). There are two applicable dose level reductions in FL, DLBCL or Richter syndrome disease cohorts: 420 mg/day (level 1 reduction) or 280 mg/day (level 2 reduction). Dose reduction information will be summarized for the number of subjects with any dose reduction (at least 1 reported dose reduction), as well as the frequency and reason of dose reduction. Number and percentage of subjects with cycle delays will also be presented.

Dose interruption for ibrutinib is defined as missing/skipped dose for ≥ 7 day. The consecutive days of dose interruption are considered as 1 dose interruption. The number and percentage of subjects with dose reduction and dose interruption will be summarized. In addition, subjects with dose modifications (i.e., reductions or interruptions) and reasons for dose modifications will be summarized.

Extent of exposure for nivolumab will be summarized for the safety population by disease type and study cohorts. Descriptive statistics (n, mean, standard deviation, median, and range) will be provided for total number of infusion, infusion duration (the interval between the start time of infusion and the end time of infusion), infusion rate interruption duration (the interval between the start time of infusion interruption and the end time of infusion interruption), and nivolumab dosing information including, total dose administered/received (the sum of actual dose administered), total number of infusions interrupted, total number of infusions skipped, total number of infusions discontinued and total number of infusion rate reductions, interval between 2 consecutive infusions of nivolumab which is defined as end date of prior cycle to first day of following cycle.

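### SAP 3.4 measures the interval between nivolumab infusions from the end of one cycle to the start of the next, so an on-schedule subject would show about 1 day instead of 14

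*SAP*

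**What the plan says.** SAP 3.4 (Extent of Exposure) lists, among the nivolumab dosing statistics, the interval between two successive infusions, "which is defined as end date of prior cycle to first day of following cycle".

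The terms in that definition are fixed elsewhere:

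- SAP 1.2 describes a cycle as "a course of treatment of 14 days starting with the intravenous administration of nivolumab on Day 1 of each cycle".
- Protocol 6.1 says that "Day 1 or start day of a new cycle is triggered by the infusion of nivolumab", and Protocol 6.1.2 that "Nivolumab will be administered on Day 1 of each 14-day treatment cycle".
- SAP 2.2 says "Each cycle is 14 days, starting from the first dose of study drug". It gives an explicit end date for one cycle only: "The end date of the last cycle is the date of the last dose of study drug received during the study".
- Protocol 6.3 sets the spacing rule: "Subjects may receive nivolumab infusions with no less than 12 days between doses". It also allows a dose up to 3 days after the scheduled date.

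**The concern.** The name and the definition describe different quantities. Two consecutive infusions fall on the first days of two consecutive cycles, so the interval between them runs from Day 1 to Day 1. The SAP instead starts the clock at the end of the earlier cycle, when most of the interval has already passed.

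What is at stake is the description of nivolumab timing. Protocol 6.4.2 allows no dose escalation or reduction of nivolumab and makes delay the main way of handling its toxicity, so the spacing of infusions is where changes to exposure would appear. Nothing else in SAP 3.4 measures it. The nivolumab dose-modification definition covers skipped doses and events during an infusion. Dose intensity is defined for ibrutinib only. Cycle delays appear only as a number and percentage of subjects, in the ibrutinib paragraph, with no duration.

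**Working it through.** This is date arithmetic. The SAP gives no numeric result for the variable, so the reference figure is the planned spacing of 14 days (Protocol 6.1.2).

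**Inputs**

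- Infusion k is on Day 1 of cycle k (Protocol 6.1 and 6.1.2, SAP 1.2).
- Cycle length is 14 days (SAP 1.2 and 2.2).
- Minimum spacing is 12 days, and the window after the scheduled date is 3 days (Protocol 6.3), so the latest in-window spacing is 14 + 3 = 17 days.
- Let D be the true interval, the date of infusion k+1 minus the date of infusion k.

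**On schedule (D = 14)**

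- Cycle k runs from Day 1 to Day 14, and infusion k+1 is on Day 15.
- Infusion to infusion: 15 - 1 = 14 days, which matches the plan.
- SAP definition: 15 - 14 = 1 day. It is 2 if both end days are counted and 0 if only the days strictly between are counted.

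**Off schedule**

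The SAP's explicit end-date rule applies to the last cycle, which has no following cycle and so never enters this variable. Earlier cycles can be read in two ways:

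- *Reading A, end fixed at Day 14.* The end date is the infusion date + 13, so the variable is D - 13.
- *Reading B, cycle lasts until the next infusion opens a new one.* The end date is the day before infusion k+1, so the variable is 1 whatever D is.

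| True interval D (days) | Reading A: D - 13 | Reading B |
|---|---|---|
| 12 (minimum spacing) | -1 | 1 |
| 14 (on schedule) | 1 | 1 |
| 17 (end of window) | 4 | 1 |
| 28 | 15 | 1 |
| 42 | 29 | 1 |

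Neither column reproduces D. The two agree only on schedule, and there both give 1 instead of 14.

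**A reading that works.** If the end date meant the end date of the infusion in the prior cycle, the variable would be D, and 14 days on schedule. The sentence refers to the end of the cycle.

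**The case against.** The strongest reply is that this is a slip of wording. The variable's name makes the intent plain, its neighbours in the same sentence are built from infusion start and end times, and a column of 1-day intervals would be noticed in the first output. That is plausible, but the text still needs correcting. The SAP uses cycle as a 14-day unit, and three programmers could defensibly produce 1, -1 or 12 for the same 12-day spacing.

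The reply also has force against some stronger conclusions that a reader might draw:

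- *That every subject will show 1 day.* This is firm for on-schedule dosing and under Reading B. Under Reading A delayed doses show more, and the SAP does not settle which reading applies.
- *That the variable is useless for checking the protocol's spacing rules.* Under Reading A the true interval is recovered by adding 13. What is lost is direct comparison with the 12-day minimum; the loss is complete only under Reading B.
- *That the variable also fails against a 42-day maximum interval.* Protocol 6.3 words the 42 days as a maximum delay between doses, which may mean time past the scheduled date or the gap between doses. On the first meaning, Reading A gives the delay plus 1 day (D - 13 = (D - 14) + 1), which is close to the limit. The 42-day figure therefore does not support the point.
- *That timing data are lost.* Protocol section 7 has the date and times of each infusion recorded in the eCRF, so the interval can always be rebuilt.

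Finally, SAP 3.4 does not say what the variable is for. Its use to describe adherence to the schedule is inferred from its name and place.

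**Conclusion.** The point stands as a definition that does not measure what it names. On schedule the error is 13 days: about 1 day shown for a true 14, or 0 to 2 by counting convention. Off schedule the value is undetermined by the SAP, being either the true interval minus 13 or a constant 1.

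This rests on cycles being anchored to the infusion, as in Protocol 6.1 and SAP 1.2. SAP 2.2 counts cycles from the first dose of either study drug and places Day 1 at the start of the run-in. Taken literally, that sets the 14-day boundaries in Cohorts B1 and B2 7 days out of step with the infusions. It is a further reason not to define an infusion interval through cycle dates.

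The consequence is minor: one descriptive exposure summary. The response rate, sample size and error rates do not depend on it.

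**What to change.** In SAP 3.4, replace the cycle-based definition with: date of nivolumab infusion k+1 minus date of nivolumab infusion k, in days. This returns 14 on schedule, 12 at the minimum spacing and 17 at the end of the 3-day window, so it can be set directly beside Protocol 6.3. It also removes the dependence on an end date for earlier cycles.

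The cost is one phrase in the SAP and the matching derivation in the exposure programming. It needs no new data and no change to treatment or visits.

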6.4. Dose Modifications

Treatment modifications may be made to both ibrutinib and nivolumab. Changes in dose apply only to ibrutinib. Nivolumab will be given at fixed dose, treatment modifications are primarily dose delays.

Adjustments of study drug dose should be overseen by the principal- or sub-investigator(s) unless an immediate safety risk is apparent. The dose adjustments are applicable to all subsequent treatment cycles.

Note: The recommendation to discontinue study therapy applies to both study drugs. If appropriate and after consultation with the Sponsor, subjects may receive ibrutinib alone. Following implementation of amendment 7, treatment with single agent ibrutinib will be discontinued and an End of Trial visit will be performed for patients not scheduled to rollover into long-term extension study CAN3001. Patients scheduled to roll over into Study CAN3001 will continue treatment.

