6.4.2. Nivolumab Dose Modifications

There will be no dose escalations or reductions of nivolumab allowed. Dose delay is the primary method for managing nivolumab-related toxicities.

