Dose modification is defined as at least 1 dose skipped or events occurred during infusion. The frequency and reason of dose skipped or events occurred during infusion will be summarized.

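### SAP 3.4 leaves dose delay out of nivolumab dose modification, so a dose given late but not recorded as skipped is missing from the count and from the table of reasons

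*SAP*

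**What the plan says.** SAP 3.4 (Extent of Exposure) defines modification for nivolumab as follows: "Dose modification is defined as at least 1 dose skipped or events occurred during infusion". The linked summary is "The frequency and reason of dose skipped or events occurred during infusion will be summarized". The descriptive list for nivolumab covers the number and duration of infusions, total dose, and infusions interrupted, skipped, discontinued or slowed. It also includes the "interval between 2 consecutive infusions of nivolumab which is defined as end date of prior cycle to first day of following cycle". It contains no delay variable and no dose intensity.

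In the ibrutinib text of the same section, the SAP adds: "Number and percentage of subjects with cycle delays will also be presented". SAP 5.1 tabulates treatment-emergent adverse events by action taken, among other breakdowns.

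The protocol treats nivolumab modification differently:

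- 6.4: "Nivolumab will be given at fixed dose, treatment modifications are primarily dose delays".
- 6.4.2 rules out escalation and reduction, and says: "Dose delay is the primary method for managing nivolumab-related toxicities".
- 6.3: "A dose given after the 3-day window is considered a dose delay".
- 6.1: "Day 1 or start day of a new cycle is triggered by the infusion of nivolumab".

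**The concern.** The SAP's definition omits the modification that the protocol names as the main one. Because a cycle starts with the infusion (protocol 6.1), a held infusion moves the cycle back. On a plain reading that dose is late, not skipped, so it meets neither limb of the SAP definition and its reason is not tabulated.

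Whether the two drugs can be combined safely is the primary objective of Part A, and the safety profile is a secondary objective. The length of a delay also matters under the protocol. An adverse event that delays dosing by more than 2 weeks in the DLT period is one of the DLT criteria (3.3.1), and a treatment delay beyond 6 weeks leads to discontinuation, with exceptions (6.4.3, 11.2).

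The two drugs are also reported unevenly. Ibrutinib has a dose intensity, an interruption threshold of at least 7 days, and reasons for its modifications. Nivolumab has none of these for delay.

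**Working it through.** The plan gives no figure to reproduce here. The check asks whether each planned output would show a nivolumab dose given late.

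**1. Modification count and reasons (SAP 3.4).** The inputs are skipped doses and infusion events. A late dose enters only if it is recorded as skipped. The SAP does not say how skipped and delayed doses are told apart.

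**2. Cycle delays (SAP 3.4).** Since the infusion starts the cycle, a late infusion is a delayed cycle, so this output does bear on nivolumab. It is a number and percentage of subjects. The term is not defined or tied to the 3-day window in protocol 6.3, and no length or reason is given.

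**3. Infusion interval (SAP 3.4).** This runs from the end of one cycle to the first day of the next. Let d be the number of days late, with the next infusion due on Day 15.

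- If the cycle is fixed at 14 days (SAP 2.2), it ends on Day 14 and the interval is (15 + d) − 14 = 1 + d. An on-time dose gives 1 day. A dose more than 3 days late (d at least 4) gives 5 days or more. A 42-day gap between infusions (d = 28) gives 29 days.
- If the cycle ends the day before the next infusion, the interval is 1 day whatever d is, and no delay shows.

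The fixed length in SAP 2.2 favors the first reading; the infusion-triggered cycle in protocol 6.1 favors the second. SAP 3.4 does not say which applies. Neither reading gives a reason.

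**4. Adverse events by action taken (SAP 5.1).** This can link an adverse event to a hold. It gives no length and omits delays not caused by an adverse event. The SAP does not list the action categories.

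**5. Illustration for one subject.** The inputs are the 14-day cycle and the 42-day maximum in protocol 6.3; the infusion counts of 10 and 6 are assumed. Planned time from first to last infusion is (n − 1) × 14. Actual time with one long gap G is (n − 2) × 14 + G. Relative intensity is planned time divided by actual time.

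| Infusions | Planned days | G = 42 (whole gap) | G = 56 (42 days beyond schedule) |
|---|---|---|---|
| 10 | 9 × 14 = 126 | 126 / (112 + 42) = 126/154 = 82% | 126 / (112 + 56) = 126/168 = 75% |
| 6 | 5 × 14 = 70 | 70 / (56 + 42) = 70/98 = 71% | 70 / (56 + 56) = 70/112 = 62.5% |

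Protocol 6.3 can be read either way on what the 42 days measure, so both columns are shown. In every case the number of infusions is the same with or without the gap, and so is the total dose at constant weight.

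**The case against.** The strongest reply is that delays are not invisible. SAP 3.4 counts subjects with cycle delays, and the position of that sentence in the ibrutinib text does not change what a cycle delay is. The infusion interval is planned, and on the fixed 14-day reading a 42-day gap would stand out at 29 days. SAP 5.1 shows the action taken for adverse events. This stands: the gap concerns the nivolumab modification summary and its reasons, not the whole of the exposure reporting.

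A second reply is that a hold may be recorded as skipped. Protocol 6.4.3 has subjects resume at the next scheduled timepoint. A 42-day gap spans three 14-day intervals, so two scheduled infusions pass; if these are coded as skipped, the SAP counts a modification and gives its reason. This also stands, and it means the same hold could be counted or not depending on coding.

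A third reply is that holding is only one of the responses to toxicity. Many rows of protocol Tables 8 and 9 say to continue, and many others say to discontinue. That is correct and limits how much can be said about frequency.

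**Conclusion.** The point holds in a limited form. The SAP definition of nivolumab dose modification omits dose delay, and the remaining outputs do not together supply the number, length and reason of delays. It matters for the description of tolerability; no efficacy result depends on it.

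A reader might infer more than this, in three ways:

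- **That most toxicity-driven modifications go uncounted.** The protocol calls delay the primary method but gives no share.
- **That a subject with a long hold would show zero modifications.** This is true only if the passed doses are not coded as skipped.
- **That an under-delivered regimen would look fully delivered.** This overlooks the cycle-delay count and the interval summary, which may show it.

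The 82% figure, and the 62.5% to 82% range across the four cases, describes a constructed subject at the longest permitted gap. It is not an expected effect in any cohort. The conclusion rests on the text of SAP 3.4 and protocol 6.1, 6.3, 6.4 and 6.4.2, and on the possibility that at least some late doses are not recorded as skipped.

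**What to change.** In SAP 3.4:

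1. Add nivolumab dose delay to dose modification, using the definition in protocol 6.3. If the scheduled date is taken as 14 days after the previous infusion, a delay is an infusion-to-infusion interval above 14 + 3 = 17 days. The SAP should state that reference date.
2. State how a delayed dose is told apart from a skipped one.
3. Tabulate the number, length and reason of delays, by disease type and study cohort as for the other exposure outputs.
4. Measure the interval from infusion date to infusion date.
5. Optionally, add relative dose intensity for nivolumab, to parallel the ibrutinib dose intensity already planned.

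The cost is SAP wording and a derived delay variable. Protocol section 7 already has the date of each infusion recorded in the eCRF. The documents do not say whether a reason is recorded for a late dose. If it is not, the SAP should say where the reason will come from, for example the action taken for the adverse event, with the remainder shown as not recorded. No treatment rule changes.
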